## **11.0 BIOMARKER, CORRELATIVE, AND SPECIAL STUDIES**

### **11.1 Tumor Biopsies**

Tumor biopsies from at least one accessible tumor lesion will be obtained from all patients during screening and after 4 doses of pembrolizumab (+/- 1 week). Where possible, tumor biopsies will be obtained at tumor progression.

Punch biopsies, surgical excisional biopsies or core biopsies are acceptable. Patients with internal visceral disease may require image guided needle biopsies.

### **11.2 Correlative Studies**

Correlative studies will be performed using PBMCs and tumor tissues collected from the patients included in the study as detailed in the laboratory manual.

These studies will include:

- Multiparameter flow cytometry to evaluate T cell phenotype and function
- Nanosorting studies of tumor biopsies
- RNAseq and exome sequencing
- Studies of T cell repertoire
- Stool samples will be used for genomic evaluation of microbiota
  - 16S ribosomal RNA (rRNA) and metagenomic sequencing will be used to characterize the complexity of the human microbiome in the stool and at multiple body sites. 16S rRNA gene sequencing is a well-established method for studying phylogeny and taxonomy of samples from complex microbiomes or environments that are difficult or impossible to study.

Prior biopsy samples including primary tumor shave/excision biopsies, sentinel lymph node biopsies, completion lymph node dissection samples will be requested from pathology. Prior tissue obtained to establish metastatic disease, as part of definitive surgical management or as part of standard of care testing prior to current therapy will also be requested. These samples will be used for immunohistochemical (IHC) and RNA sequencing studies to evaluate immune responses and gene signatures associated with improved clinical outcome.

## APPENDICES

### Appendix 1: FMT Recipient (or Donor) Screening Questionnaire

Dear \*\*\* :

You have been identified as a potential donor for a medical procedure called fecal microbiota transplantation (FMT, or stool transplantation). FMT is a relatively new medical procedure that has been used to treat patients with *C. difficile* infections (CDI) – a diarrheal illness caused by antibiotics that kill the normal stool bacteria of the human gastrointestinal tract. The composition of gut bacteria has been shown to mediate outcomes to PD-1 inhibitor therapy in animal models of melanoma. You have been identified by [name] and [name] as a potential stool donor.

Your doctors are conducting a study in which patients with advanced melanoma whose cancer **is not responding** to PD-1 therapy receive FMT. In this study, selected patients will receive an extract from your frozen stool sample. Are you interested in learning more about how you can participate as a donor for FMT? **YES, PLEASE / NO THANKS**

*If no, you do not need to answer any more questions. Please return this form to the person who gave it to you or to the return address at the end of this form. If yes, please continue to answer the following questions:*

**Name (please print):**

**Date of birth:**

**Gender:**           MALE / FEMALE

**Telephone number(s):**

**Date Completed:**

**Time Completed:**

---

The answers to the following questions will be used by our stool transplant physician to determine if your feces can be used for a stool transplant. The answers to some but not all questions may disqualify you as a donor. Please answer the questions truthfully. The answers that you give will NOT be shared with the person you are donating to or appear in his/her chart.

1. Are you at least 18 years old?           **YES/NO**
2. Except for birth control, do you take any prescription medications?           **YES/NO**
3. What is your height in feet and inches?
4. What is your weight in pounds?
5. Have you ever donated blood before?
  - a. If yes, have you even been notified by the blood bank of any positive testing for infectious conditions such as hepatitis C or HIV?
  - b. If no, have you attempted to donate blood previously but asked not to donate for medical reasons ?

Please answer the following **YES / NO** questions to the best of your ability:

**In the past 6 weeks**

6. Female donors: Have you been pregnant or are you pregnant now? **YES / NO / I AM MALE**

**In the past 8 weeks have you:**

7. Donated blood, platelets or plasma? **YES / NO**
8. Had any vaccinations or other shots? **YES / NO**
9. Had contact with someone who had a smallpox vaccination? **YES / NO**

**In the past 3 months have you:**

- 10. Used any antibiotics? **YES / NO**
- 11. Had any diarrhea? **YES / NO**
- 12. Had any vomiting? **YES / NO**
- 13. Had any food poisoning? **YES / NO**
- 14. Had any fevers? **YES / NO**
- 15. Been hospitalized (long enough to stay overnight)? **YES / NO**
- 16. Been seen in an emergency room or urgent care visit? **YES / NO**

**In the past 12 months have you**

- 17. Had a blood transfusion? **YES / NO**
- 18. Had a transplant such as organ, tissue, or bone marrow? **YES / NO**
- 19. Had a graft such as bone or skin? **YES / NO**
- 20. Come into contact with someone else's blood? **YES / NO**
- 21. Had an accidental needle-stick? **YES / NO**
- 22. Had sexual contact with anyone who has HIV/AIDS or has had a positive test for the HIV/AIDS virus?  
**YES / NO**
- 23. Had sexual contact with a prostitute or anyone else who takes money or drugs or other payment for sex? **YES / NO**
- 24. Had sexual contact with anyone who has ever used needles to take drugs or steroids, or anything not prescribed by their doctor? **YES / NO**
- 25. Had sexual contact with anyone who has hemophilia or has used clotting factor concentrates?  
**YES / NO**
- 26. Had sexual contact with a person who has hepatitis? **YES / NO**
- 27. Lived with a person who has hepatitis? **YES / NO**
- 28. Had a tattoo? **YES / NO**
- 29. Had ear or body piercing? **YES / NO**
- 30. Had or been treated for syphilis or gonorrhea? **YES / NO**
- 31. Been in juvenile detention, lockup, jail, or prison for more than 72 hours? **YES / NO**

**In the past three years have you**

- 32. Been outside the United States or Canada? **YES / NO**

**From 1980 through 1996,**

- 33. Did you spend time that adds up to three (3) months or more in the United Kingdom? (Northern Ireland, Wales, Scotland, England [sometimes called Great Britain])? **YES / NO**
- 34. Were you a member of the U.S. military, a civilian military employee, or a dependent of a member of the U.S. Military? **YES / NO**

**From 1980 to the present, did you**

- 35. Spend time that adds up to five (5) years or more in Europe? **YES / NO**
- 36. Receive a blood transfusion in the United Kingdom or France? **YES / NO**

**From 1977 to the present, have you:**

- 37. Received money, drugs, or other payment for sex? **YES / NO**
- 38. Male donors: had sexual contact with another male, even once? **YES / NO / I AM FEMALE**

**COVID-19 Related Exposure**

- 39. Have you at any time been diagnosed with laboratory-confirmed SARS-CoV-2 infection?
- 40. Have you at any time experienced symptoms of COVID-19 (e.g., fever, cough, shortness of breath) not explained adequately by another diagnosis?
- 41. Have you been exposed to a suspected or confirmed case of COVID-19 or SARS-CoV-2 infection?

**Have you EVER:**

42. Had *C. difficile* infection previously? **YES / NO**
43. Had a positive test for the HIV/AIDS virus? **YES / NO**
44. Used needles to take drugs, steroids, or anything not prescribed by your doctor? **YES / NO**
45. Used clotting factor concentrates? **YES / NO**
46. Had hepatitis? **YES / NO**
47. Had malaria? **YES / NO**
48. Had Chagas' disease? **YES / NO**
49. Had babesiosis? **YES / NO**
50. Received a dura mater (or brain covering) graft? **YES / NO**
51. Had any type of cancer, including leukemia? **YES / NO**
52. Had parents, brothers, sisters, or children diagnosed with cancer? **YES / NO**
53. Had any problems with your heart or lungs? **YES / NO**
54. Had a bleeding condition or a blood disease? **YES / NO**
55. Had sexual contact with anyone who was born in or lived in Africa? **YES / NO**
56. Been in Africa? **YES / NO**
57. Been in the Caribbean? **YES / NO**
58. Been in Central or South America (anywhere south of the US Border including Mexico)? **YES / NO**
59. Been elsewhere outside the US? **YES / NO**
60. Had relatives who had Creutzfeldt-Jakob disease? **YES / NO**
61. Been previously tested for HIV or viral hepatitis? **YES / NO**
62. Tested positive for MRSA (methicillin resistant *Staphylococcus aureus*), VRE (vancomycin resistant enterococcus) or other resistant bacteria? **YES / NO**
63. Had diarrhea lasting for longer than 2 weeks? **YES / NO**
64. Had irritable bowel syndrome? **YES / NO**
65. Had chronic constipation? **YES / NO**
66. Had chronic pain? **YES / NO**

A physician will review this form to determine if you can be scheduled for a screening visit with an infectious disease physician for additional questions. If you answer in the positive to questions 39-41, you will be referred to an infectious disease physician for additional evaluation. If you are eligible based on this visit, you will be scheduled for laboratory testing. If you are eligible and willing to participate as a potential stool donor, you will be asked to do the following:

- 1) Schedule a screening visit with a physician in Oakland at the Falk Medical Building
- 2) Have blood tests and stool tests collected for testing
- 3) Donate stool either in person or off-site on the morning of the scheduled procedure.

Please mail this form to:

**Serologic tests (blood, stool, nasal swabs) in donors will be performed per Section 4.2.3. (Figure 4).**

Blood	Stool	Nasal
#HIV antibody \$Hepatitis A total Ab #Hepatitis B surface Ab, core Ab, surface Ag #Hepatitis C Ab #Syphilis screening serology Strongyloides stercoralis Ab #Entamoeba histolytica Ab #HTLV-1 and HTLV-2 Ab *CMV IgG *EBV AB panel *HSV-1 IgG *HSV-2 IgG *HHV-6 IgG *JC virus Ab	@Bacteria 
 
• Campylobacter
 
• Clostridium difficile
 
• E.coli H7
 
• Helicobacter pylori
 
• Salmonella
 
• Shigella
 
• Vibrio
 
• Yersinia
 
 @Viruses 
 
• Rotavirus
 
• Adenovirus
 
• Norovirus
 
• SARS-CoV-2
 
 @Fungi/Parasites 
 
• Giardia
 
• Cryptosporidia
 
• Ova/parasites
 
 #MDRO 
 
• Vancomycin Resistant Enterococci (VRE)
 
• Carbapenem Resistant Enterobacteriaceae (CRE)
 
• Extended Spectrum Beta-Lactamase producing bacteria (ESBLs)
 
	*MRSA %SARS-CoV-2 (will be done 2 weeks before)

% if positive, ineligible to donate FMT and will result in reflex referral to Infectious Disease Physician.
 
 
• Determination of "SARS-CoV-2 negative" status will be made on specimens obtained at two timepoints: 1st sample collected at least 14 days before stool sample donation, and a 2nd sample collected at least 14 days after stool sample donation.
 
• As the turnaround of the test is 48-72 hours, the stool sample will be released for FMT use no sooner than 48-72 hours after 2nd test results and donor is deemed "SARS-CoV-2 negative".
 
• Donors who were excluded based on based on screening and/or testing as described in 3.1 and 4.1.1-4.1.2 above will not be allowed to donate stool specimens for use in this study at this time. This is subject to subsequent revision should stool-specific SARS-CoV-2 testing become available.
 
 
#if positive, ineligible to donate FMT
 
*if positive, eligible to receive FMT from seropositive or negative donors (i.e. donors who are similarly positive or who test negative).
 
@if positive, must be repeated and be tested negative prior to determination of eligibility (NOTE: exceptions may be made in the case of asymptomatic recipients who test positive AFTER consultation with PI).
 
§if positive, must be followed by Hepatitis A IgG and IgM.
 
 
• For donors: IgM positive donors are ineligible to donate. IgG positive donors are eligible to donate.
 
• For recipients: IgM/G status does not affect ability to receive FMT.
 
		

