- 4.1.2. Stool test: DSL COVID-19 stool assay evaluates for the presence of three coronavirus genes: SARS-CoV-2 membrane (M), SARS-CoV-2 spike (S) and SARS-CoV-2 nucleocapsid (N). Following adequate detection of RNaseP in a test sample, detection of 1 of the viral genes is sufficient for a positive test result. Due to the discontinuous transcription of all coronaviruses that results in the presence of the capsid gene in a vast majority of the mRNA populations as well as in the full-length viral genome, detection of the capsid gene in the absence of additional genes is expected. The lower limit of detection (LLoD) for each viral gene target was determined by testing serial dilutions of the SARS-CoV-2 genomic isolate in triplicate and is summarized in the DSL COVID-19 validation summary. These data indicate that the LLoD for viral spike (S) and membrane (M) detection is 104 genomic equivalents/mL while the LLoD for viral capsid (N) detection is 103 genomic equivalents/mL. In addition, the observation that the mean CT value for each of the determined LLoDs are very low (close to 40 cycles), it is likely that any signal obtained below a CT of 38 is below the LLoD for the viral target genes and should be disregarded for analytic purposes.
- 4.2. Determination of "SARS-CoV-2 negative" status will be made on nasopharyngeal, blood and stool specimens obtained at two timepoints (every 2 weeks for up to 12 weeks): 1st sample collected at least 14 days before stool sample donation, and a 2nd sample collected at least 14 days after stool sample donation.
- 4.3. As the turnaround of the test is 48-72 hours, the stool sample will be released for FMT use no sooner than 48-72 hours after 2nd test results and donor is deemed "SARS-CoV-2 negative".
- 4.4. Candidate donors with discordant stool and NP SARS-CoV-2 results will be excluded.
- 4.5. Candidate donors excluded based on based on screening and/or testing as described in 3.1 and 4.1.1-4.1.2 above will not be allowed to donate stool specimens for use in this study at this time. This is subject to subsequent revision should stool-specific SARS-CoV-2 testing become available.

Inclusion criteria "PD-1R– at interest population":

1. Documented history of metastatic melanoma (or other malignancies) treated with pembrolizumab or nivolumab or other PD-1/PD-L1 inhibitors.
2. Currently in complete/partial remission with duration of complete/partial remission  $\geq 6$  months since initiation of therapy.

Exclusion criteria:

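### Appendix 2 lets the principal investigator except asymptomatic recipients with a positive stool SARS-CoV-2 test, whom recipient exclusion 14.1 makes ineligible without exception

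*Combined protocol and SAP*

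**What the plan says.** Appendix 2 lists SARS-CoV-2 twice. In the nasal column the entry carries '%': "SARS-CoV-2 (will be done 2 weeks before". In the stool column it is the last item in the virus group, whose heading carries '@'; the stool entry has no mark of its own.

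The two notes differ in kind:

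- '%': "if positive, ineligible to donate FMT and will result in reflex referral to Infectious Disease Physician". This lead sentence speaks of donating only.
- '@': "if positive, must be repeated and be tested negative prior to determination of eligibility", followed by a remark that "exceptions may be made in the case of asymptomatic recipients who test positive", provided the principal investigator is consulted first.

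The table serves both populations. Sections 7.1.3 and 7.1.5.2 send recipients to Appendix 2 for infectious screening before FMT. For donors, the table's heading refers the tests back to Section 4.2.3.

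The recipient rule is in Section 5.1.2. A patient who meets any listed criterion is ineligible, and criterion 14.1 is a positive SARS-CoV-2 RT-PCR on a nasopharyngeal and/or stool specimen. Neither the criterion nor the lead-in mentions a retest or an exception.

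The donor rules are in Section 4.2.3.1. For the stool assay, once the internal control is detected, "detection of 1 of the viral genes is sufficient for a positive test result" (item 4.1.2). Item 4.4 adds: "Candidate donors with discordant stool and NP SARS-CoV-2 results will be excluded".

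**The concern.** Staff who clear a recipient for colonoscopic FMT work from the Appendix 2 table. For an asymptomatic patient with a positive stool SARS-CoV-2 result, the table tells them that an exception can be agreed with the principal investigator. The eligibility criteria say that this patient cannot take part.

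At stake are the safety screen for patients with advanced cancer and the regularity of enrolment. Section 10.8 allows a deviation without prior IRB approval only to remove an immediate hazard. A team that used the '@' exception in good faith would be enrolling an ineligible patient while following a page of the protocol.

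**Working it through.** There is no figure to reproduce; the check is a comparison of rules for the same test result.

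**Recipient, stool positive, no symptoms**

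1. Which table applies? Sections 7.1.3 and 7.1.5.2 both point to Appendix 2, so the marks in that table apply to recipients.
2. What does the mark say? Under '@', the positive test is repeated and must be negative before eligibility is decided. Separately, the principal investigator may be consulted about an exception for an asymptomatic recipient who tests positive.
3. What does Section 5.1.2 say? Under 14.1 the patient is ineligible. The criterion turns on the RT-PCR result and names stool; symptoms do not enter into it.
4. Can the two be reconciled? In part. Criterion 14 is headed by active infection and/or exposure, so one could argue that a patient who later tests negative no longer meets it. That reading could accommodate the retest half of '@'. It cannot accommodate the exception half, which concerns a patient who is positive.
5. Does '%' cover the recipient? No. Its lead sentence covers donating only, so changing the mark alone would leave the recipient without a rule in the table.

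**Donor, stool positive**

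| Nasopharyngeal result | Rule that applies | Outcome |
|---|---|---|
| Negative | Item 4.4, discordant results | Excluded |
| Positive | '%' note on the nasal test | Ineligible to donate |

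Both branches end in exclusion. Other text points the same way:

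- Item 4.2 requires negative status on nasopharyngeal, blood and stool specimens at two timepoints.
- Item 4.3 releases stool only after the second results, once the donor is deemed negative. A bullet under '%' repeats this.
- Item 4.5, and a further '%' bullet, say that donors excluded on "screening and/or testing as described in 3.1 and 4.1.1-4.1.2 above will not be allowed to donate stool specimens for use in this study". Item 4.1.2 is the stool test.
- Exclusion 1 bars suspected or confirmed infection or exposure.
- The donor figure puts SARS-CoV-2 in the group that cannot donate and leaves it out of the viruses that may be retested.

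The '@' mark on the donor's stool test therefore conflicts with its surroundings as a label, but does not open a route to donation.

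**The case against.** The best defence is that a specific exclusion outranks a general footnote. Criterion 14.1 names stool RT-PCR; the '@' exception is permissive, reads as written for a group of enteric organisms, and requires consultation. Section 7.1.1.2 has every criterion reviewed for every subject, so a careful team would stop at 14.1. That is a fair account of how the conflict ought to be resolved. It does not remove the conflict: the protocol states no order of precedence between the table and the criteria, and the person consulted under '@' is given no sign that SARS-CoV-2 is outside the exception.

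A second defence is that the finding rests on a footnote mark in a table read from PDF. Marks in this table are not wholly reliable: the one beside hepatitis A differs from the one at its footnote. The caution is reasonable, but SARS-CoV-2 sits inside an intact list under the virus heading, and '@' on the bacteria, virus and fungi/parasite groups agrees with the retest group in the donor figure.

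A reader might go further and infer that Appendix 2 lets a stool-positive donor give material after a negative repeat. The documents do not support that. The '@' note makes a negative repeat a precondition for deciding eligibility, not a grant of it, so the stricter donor rules still apply. The table's heading itself refers donor testing to Section 4.2.3, and the product stays on hold until the donor is deemed negative.

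**Conclusion.** The concern holds for recipients: Appendix 2 offers an exception for a positive, asymptomatic patient that exclusion 14.1 does not allow. For donors it is a labelling mismatch with no operative gap. The conclusion assumes that the '@' on the virus heading is as printed.

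Its size is one table entry and one note. How many patients it could touch cannot be computed: the protocol gives no stool-positivity rate and no number to be screened. A reader might take the planned 20 (13 in stage 1 plus 7 in stage 2) as the number exposed to the rule, but that is the evaluable target; patients screened and turned away fall outside it.

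The decision rule, its error rates and the response endpoint are unchanged. This is an eligibility and safety inconsistency that should be fixed because the correction is nearly free.

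**What to change.** In Appendix 2, mark stool SARS-CoV-2 '%' instead of '@', and extend the '%' note itself with: *Recipients: a positive nasopharyngeal or stool SARS-CoV-2 RT-PCR is exclusionary under 5.1.2 criterion 14.1; the @ retest/PI exception does not apply.*

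Both edits are needed, and the sentence belongs under '%'. Once the item is moved, a reader checking a recipient's result will look there and would otherwise find only donor wording.

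The cost is one symbol and one sentence. In use, an asymptomatic or falsely positive person is not enrolled or does not donate, which 14.1 and item 4.4 already require.

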## Appendix 3: Dietary History Questionnaire for Microbiome Sampling

Version date 1/17/19

### Dietary History Questionnaire

This is a food frequency questionnaire (FFQ) modified for patients receiving immune checkpoint blockade (ICB) therapy. This FFQ is modified from the publically available Diet History Questionnaire (DHQ) developed by staff at the Risk Factor Assessment Branch (RFAB) of the National Institutes of Health. This FFQ consists of a finite list of foods and beverages with response categories to indicate usual frequency of consumption over the time period queried.

This FFQ is designed to be completed every time you visit receive treatment or are in to see your physician. It can either be done at home or at each study visit.

### Demographics

First Name \_\_\_\_\_

Last Name \_\_\_\_\_

Sex \_\_\_\_\_

### Current Medications (including supplements).

For this question, please report the names and dosages of all prescription medications you take. Please include supplements and any as-needed (prescription or over the counter) medicines you take at least weekly.

Current Medications (including supplements and vitamins).

### Visits

For this question, please indicate today's date and your weight in pounds (lbs).

Date \_\_\_\_\_

Weight (in lbs) \_\_\_\_\_

### Beverages

#### What beverages do you drink?

For this question, please estimate the frequency and quantity of the item in question. Frequency is estimated as: 1-2 times per week, 3-4 times per week, 5-6 times per week, 1 time per day, 2-3 times per day, 4-5 times per day, 6 or more times per day.

Please quantify intake in 8oz terms. Please choose only one answer for each question.

Do you drink beverages?

- No
- Yes

Do you drink fruit and/or vegetable juices?

- No
- Yes

How often do you drink fruit juice?

- <1 time per week
- 1-2 times per week
- 3-4 times per week
- 5-6 times per week
- 1 time per day
- 2-3 times per day
- 4-5 times per day
- 6 or more times per day

How often do you drink vegetable juice?

- <1 time per week
- 1-2 times per week
- 3-4 times per week
- 5-6 times per week
- 1 time per day
- 2-3 times per day
- 4-5 times per day
- 6 or more times per day

How often do you drink other fruit/vegetable juice?

- <1 time per week
- 1-2 times per week
- 3-4 times per week
- 5-6 times per week
- 1 time per day
- 2-3 times per day
- 4-5 times per day
- 6 or more times per day

Do you drink milk or milk-based beverages?

- No
- Yes

How often do you drink milk including flavored milk (chocolate, strawberry etc.)?

- <1 time per week
- 1-2 times per week
- 3-4 times per week
- 5-6 times per week
- 1 time per day
- 2-3 times per day

- 4-5 times per day
- 6 or more times per day

How often do you drink milk based meal replacements (Boost, Ensure, Carnation Instant Breakfast)??

- <1 time per week
- 1-2 times per week
- 3-4 times per week
- 5-6 times per week
- 1 time per day
- 2-3 times per day
- 4-5 times per day
- 6 or more times per day

Do you drink coffee and/or tea?

- No
- Yes

How often do you drink coffee and/or tea?

- <1 time per week
- 1-2 times per week
- 3-4 times per week
- 5-6 times per week
- 1 time per day
- 2-3 times per day
- 4-5 times per day
- 6 or more times per day

Do you typically add sugar (or sugar equivalents such as Equal, Splenda etc.) to your coffee and/or tea?

- No
- Yes

How much sugar (or sugar equivalents such as Equal, Splenda etc.) do you add?

- 1 sachet
- 2 sacets
- 3 or more sachets

Do you typically add milk (or milk equivalents such as half-and-half, creamer etc.) to your coffee and/or tea?

- No
- Yes

How much milk (or milk equivalents such as half-and-half, creamer etc.) do you add?

- 1 sachet

- 2 sachets
- 3 or more sachets

Do you drink soda/pop or other carbonated beverages?

- No
- Yes

How often do you drink soda/pop or other carbonated beverages (including diet soda)?

- <1 time per week
- 1-2 times per week
- 3-4 times per week
- 5-6 times per week
- 1 time per day
- 2-3 times per day
- 4-5 times per day
- 6 or more times per day

Do you drink sports/energy drinks (including diet variety) such as Gatorade, Powerade etc.?

- No
- Yes

How often do you drink sports/energy drinks (including diet variety) such as Gatorade, Powerade etc.?

- <1 time per week
- 1-2 times per week
- 3-4 times per week
- 5-6 times per week
- 1 time per day
- 2-3 times per day
- 4-5 times per day
- 6 or more times per day

Do you drink alcohol (including beer, spirits, wine)?

- No
- Yes

How often do you drink beer?

- <1 time per week
- 1-2 times per week
- 3-4 times per week
- 5-6 times per week
- 1 time per day
- 2-3 times per day
- 4-5 times per day

- 6 or more times per day

How often do you drink wine?

- <1 time per week
- 1-2 times per week
- 3-4 times per week
- 5-6 times per week
- 1 time per day
- 2-3 times per day
- 4-5 times per day
- 6 or more times per day

How often do you drink mixed drinks and/or liquor?

- <1 time per week
- 1-2 times per week
- 3-4 times per week
- 5-6 times per week
- 1 time per day
- 2-3 times per day
- 4-5 times per day
- 6 or more times per day

